## **2.5 MULTIPLICITY ADJUSTMENT**

No multiplicity adjustment is planned for the primary effectiveness endpoints of DCIVA and defocus since only the DCIVA endpoint requires hypothesis testing. One-sided testing with alpha level of 0.025 is planned for this endpoint. No multiplicity adjustment is planned for the safety endpoints.

Due to multiple secondary endpoints, a closed-form hierarchical approach will be used to evaluate statistical significance. Secondary endpoints will be tested in the following order:

1. Monocular distance corrected near visual acuity at 40cm
2. Overall spectacle independence

Since one-sided testing will be performed, an alpha level of 0.025 will be used. The hierarchical approach for p-value adjustment is based on a statistically significant p-value for each test. Therefore, if other clinical criteria associated with the endpoint are not met but statistical significance is achieved, testing will proceed hierarchically to the following endpoint.

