### **Secondary Effectiveness Endpoints**

Due to multiple endpoints, a closed-form hierarchical approach will be used.

Secondary endpoints will be tested in order as follows:

---

 Rom D and B. Holland. (1995). A new closed multiple testing procedure for hierarchical families of hypotheses. Journal of Statistical Planning and Inference 46:265-275

 Rom D, R. Costello, and L. Connell. (1994). On closed test procedures for dose-response analysis. Statistics in Medicine 13:1583-1596

 Marcus R, E. Peritz, and K. Gabriel. (1976). On closed testing procedures with special reference to ordered analysis of variance. Biometrika 63:655-660.

 Huque M and A Sankoh. (1997). A reviewer's perspective on multiple endpoint issues in clinical trials. Journal of Pharmaceutical Sciences 7:545-564.

MONOCULAR DISTANCE-CORRECTED NEAR VISUAL ACUITY (DCNVA) AT 40 CM

The first secondary effectiveness endpoint is mean (LogMAR), monocular DCNVA under photopic conditions at 40 cm at 6 months. Comparisons between lens groups will be performed using a one-sided, t-test with an alpha level of 0.025. Note that a lower LogMAR value is a better acuity and a higher LogMAR value is a poorer acuity. The null hypothesis is that the mean monocular DCNVA LogMAR value for the Model ZHR00 eyes is worse than or equal to that for control eyes. The alternate hypothesis is that the mean monocular DCNVA LogMAR value for Model ZHR00 is better than that for control eyes.

$H_0: \mu_c - \mu_t \leq 0$  (ZHR00 is worse than (higher LogMAR) or equal to control)

$H_1: \mu_c - \mu_t > 0$  (ZHR00 is better (lower LogMAR) than control)

where

$\mu_t$  = the mean LogMAR DCNVA for Model ZHR00 lens

$\mu_c$  = the mean LogMAR DCNVA for control lens

Reject the null hypothesis if one-sided p-value  $\leq 0.025$ .

The success criterion is a statistically significantly lower mean LogMAR DCNVA for ZHR00 compared to ZCB00 ( $p \leq 0.025$ ). In addition, clinical significance will be determined by the median DCNVA of ZHR00 being at least 0.3 LogMAR.

OVERALL SPECTACLE INDEPENDENCE VIA BINOCULAR QUESTIONNAIRE

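### Neither document makes the secondary testing sequence conditional on a significant primary DCIVA test, so error over the tested primary and secondary endpoints can exceed one-sided 0.025

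*SAP*

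**What the plan says.** SAP 2.5 handles the primary and secondary endpoints in two separate paragraphs.

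- **Primary.** "No multiplicity adjustment is planned for the primary effectiveness endpoints of DCIVA and defocus since only the DCIVA endpoint requires hypothesis testing". The next sentence sets the level: "One-sided testing with alpha level of 0.025 is planned for this endpoint".
- **Secondary.** The second paragraph begins "Due to multiple secondary endpoints, a closed-form hierarchical approach" and continues "Secondary endpoints will be tested in the following order". The numbered list holds DCNVA at 40 cm, then overall spectacle independence. The level is again the full one: "Since one-sided testing will be performed, an alpha level of 0.025 will be used".
- **Moving down the list.** Progression depends on statistical significance only: "if other clinical criteria associated with the endpoint are not met but statistical significance is achieved, testing will proceed hierarchically to the following endpoint".

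Protocol 20.2 introduces the hierarchy under its secondary effectiveness heading: "Due to multiple endpoints, a closed-form hierarchical approach will be used", then "Secondary endpoints will be tested in order as follows". It has the same two endpoints in the same order. The individual endpoint sections (SAP 5.1.1, 5.2.1 and 5.2.2, and their counterparts in Protocol 20.2) each give a rejection rule at one-sided 0.025. None refers to the result of another endpoint. SAP 2.3 points to Section 2.5 for the primary and secondary endpoints that relate to product claims.

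**The concern.** A fixed sequence protects only the hypotheses inside it. Here it starts at DCNVA, so the plan has two entry points at the full 0.025: DCIVA on its own, and DCNVA followed by spectacle independence. SAP 2.5 says what a missed clinical criterion does to the sequence (nothing), but not what a failed primary test does to it.

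Two things are at stake. First, one-sided error over the three tested effectiveness hypotheses is not held at 0.025. Second, if DCIVA fails, one reader could report DCNVA as a confirmatory result and another could treat it as descriptive, and the text would not settle which is right. That rule should be fixed before results are seen, particularly as the SAP associates both sets of endpoints with product claims.

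**Working it through.** **Inputs from the documents.** DCIVA, DCNVA and spectacle independence are each tested at one-sided 0.025 (SAP 2.5, 5.1.1, 5.2.1, 5.2.2). The planning values for DCIVA and DCNVA are a 1-line difference, SD 1.6 lines and 100 per group (SAP 7.1, 7.2). The correlation between the DCIVA and DCNVA test statistics is not given, so I assume a range of 0 to 0.9. Both are measured in the same first eyes, which makes a positive value plausible.

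**Step 1: the plan's own power figure.** The standardised difference is 1 / (1.6 × √(2/100)) = 4.42. Power is Φ(4.42 − 1.96) = 0.993, or 0.9926 from the noncentral t distribution. This agrees with the stated figure of over 90%.

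**Step 2: false rejection without a gate, DCIVA and DCNVA both null.** The chance of at least one false rejection is P(Z1 > 1.96 or Z2 > 1.96). Under independence it is 1 − 0.975² = 0.0494. For positive correlation the bivariate normal gives:

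| Assumed correlation | At least one false rejection |
|---|---|
| 0 | 0.0494 |
| 0.3 | 0.0476 |
| 0.5 | 0.0454 |
| 0.7 | 0.0417 |
| 0.9 | 0.0352 |

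The bound under any dependence is 0.025 + 0.025 = 0.05.

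**Step 3: other null configurations.** These were simulated with 2,000,000 draws per setting, treating all three tests as normal.

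- DCIVA and spectacle independence null, DCNVA truly different: 0.0491 under independence. Fisher's exact test is conservative, so the real figure is lower. Exact enumeration at 100 per group, over assumed common rates of 5% to 50%, gives Fisher rejection rates of 0.010 to 0.020. That puts the total at about 1 − 0.975 × 0.990 = 0.035 to 1 − 0.975 × 0.980 = 0.044.
- Only DCIVA null: 0.025.
- DCIVA truly different, both secondary endpoints null: 0.025. The existing sequence is sufficient here.

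**Step 4: with a DCIVA gate.** In the same simulations the error was 0.0248 to 0.0251 in every configuration, that is, 0.025 within simulation error.

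**Step 5: cost of the gate.** The power lost for DCNVA cannot exceed the chance that DCIVA fails: 1 − 0.993 = 0.007, or 0.7 percentage points.

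**Step 6: rejection against full success.** Success also needs a clinical criterion. For spectacle independence, requiring both Fisher p ≤ 0.025 and an observed difference of at least 25 percentage points gives at most 0.00025 in the same enumeration.

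**The case against.** The strongest reply is that the plan breaks no promise. SAP 2.5 gives the reason for its hierarchy as the multiplicity of secondary endpoints. One primary test at 0.025 and one fixed secondary sequence at 0.025 each hold their own level. The cross-reference in SAP 2.3 does not commit the sponsor to a joint 0.025. This stands. A reader might infer that the plan violates its own stated error control, and the documents do not support that.

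A second reply is that silence is not permission. Neither document expressly says that secondary testing goes ahead after DCIVA fails. The Protocol's introduction speaks of multiple endpoints without the word secondary, though it sits under the secondary heading, and the sponsor may have intended the usual gate. This stands in part: the gate is absent by omission. An unwritten gate still does not bind the analysis.

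Third, 0.049 is easily read as the probability of a false product claim. It is not. It is a false-rejection rate under independence, which is the less plausible case for two acuities in the same eyes. Full success also requires the median criteria for DCIVA (0.2 LogMAR) and DCNVA (0.3 LogMAR), or the 25-point difference for spectacle independence. This stands, and for spectacle independence the reduction is very large (step 6). It does not remove the issue for declared significance, because SAP 2.5 lets testing proceed on the p-value alone.

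Finally, under the planning values DCIVA fails in only about 0.7% of trials. That is true, but error control concerns the case where DCIVA has no effect, which those values exclude.

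**Conclusion.** The point holds as a gap in the testing rule. Neither SAP 2.5 nor Protocol 20.2 makes the secondary sequence depend on DCIVA, so followed literally the plan allows DCNVA to be declared significant after the primary test fails.

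The excess error arises only if DCIVA and at least one secondary endpoint are truly null. With DCIVA and DCNVA null, the chance of at least one false rejection is about 0.035 to 0.045 at correlations of 0.9 to 0.5, and at most 0.049 with non-negative correlation, against 0.025 for a single gated sequence. The correlations are assumptions. The chance of a false full success claim is lower than these figures; it was computed here only for spectacle independence. If DCIVA truly differs, the plan already holds the secondary error at 0.025. The issue merits a clarifying amendment and does not call the design or sample size into question.

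**What to change.** Put the same rule in SAP 2.5 and Protocol 20.2: DCNVA is tested only if the DCIVA one-sided p-value is at most 0.025, and spectacle independence is tested only if DCNVA is also significant at one-sided 0.025.

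Add how the other primary criteria bear on the gate. Consistent with what SAP 2.5 already says for the secondary steps, the gate should rest on the DCIVA p-value, with the DCIVA median criterion and the defocus criterion judged separately for primary success.

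The cost is a short addition to each document, with no change to sample size, visits or data collection. The downside is that no confirmatory DCNVA or spectacle-independence result is available if DCIVA fails. Under the planning values that costs DCNVA at most about 0.7 percentage points of power.

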## **2.6 SITE DIFFERENCES**

For the primary and secondary effectiveness endpoints, data will be reported by site. A mixed effects analysis will be used for primary DCIVA and both secondary effectiveness endpoints. The mixed model will be used with IOL group as a fixed effect and site and site by group interaction as random effects. If the interaction term is significant at the 0.15 level than further examination of effects of site or further data stratification by site will be evaluated. Since there is no inferential statistics for the defocus curve primary effectiveness endpoint, only graphs (defocus curve by site) will be presented for the site analysis. Baseline demographic data will also be reported by site.

# **3 ACCOUNTABILITY/DEMOGRAPHICS**

## **3.1 ACCOUNTABILITY**

The number of enrolled subjects will be tabulated by site for first and second eyes. Subject accountability will be summarized as a frequency distribution by scheduled visits. A frequency table by IOL will be generated, showing the number of available eyes (those in interval and outside of the interval) and the number of missing and active subjects.

## **3.2 DEMOGRAPHICS**

Subject demographic data including age, sex, race, and eye color will be presented by IOL group. Age will be determined at the time of the preoperative visit and will be categorized by less than 60, 60 to 69, 70 to 79, and equal to or older than 80 years old. In addition, age will be summarized with descriptive statistics. The frequency distributions of sex, race, and iris color will also be tabulated.

Comparisons between IOL groups will be performed using Fisher's exact test for demographic categorical data. The null hypothesis is that there is no difference in the proportion with specific responses between IOL groups, whereas the alternative hypothesis is that there is a difference in at least one proportion between IOL groups.

For comparisons between IOL groups for mean age, the two-sample t-test will be used. The null hypothesis is that there is no difference in mean values between IOL groups, whereas the alternative hypothesis is that there is a difference in mean values between IOL groups. Two-sided testing with an alpha level of 0.05 will be used for all demographic variables.

## 4 PREOPERATIVE/OPERATIVE PARAMETERS

Preoperative and operative parameters for first and second eyes will be reported for each IOL model. The frequency and proportion of eyes with selected responses will be tabulated for categorical data with descriptive statistics used for continuous data. Statistical comparisons between IOL groups will be performed as described above for demographic data. Two-sided testing with an alpha level of 0.05 will be used for all preoperative and operative parameters.

## 5 POSTOPERATIVE ANALYSES – PRIMARY AND SECONDARY EFFECTIVENESS ENDPOINTS

### 5.1 PRIMARY EFFECTIVENESS ENDPOINTS

#### 5.1.1 MONOCULAR DISTANCE CORRECTED INTERMEDIATE VISUAL ACUITY (DCIVA)

The first primary effectiveness endpoint is mean (logMAR) first-eye, monocular, distance corrected intermediate visual acuity (66 cm) at 6 months postoperative. Results will be reported by lens group for first eyes using one-sided, two-sample t-tests with alpha level of 0.025. Note that a lower LogMAR value is a better acuity and a higher LogMAR value is a poorer acuity. The null hypothesis is that the mean LogMAR value for ZHR00 eyes is worse than or equal to that for control eyes. The alternative hypothesis is that the mean for ZHR00 eyes is better than that for control eyes.

$H_0: \mu_c - \mu_t \leq 0$  (ZHR00 is worse than (higher logMAR) or equal to control)

$H_1: \mu_c - \mu_t > 0$  (ZHR00 is better (lower logMAR) than control)

where

$\mu_t$  =mean LogMAR DCIVA for ZHR00

$\mu_c$ = mean LogMAR DCIVA for ZCB00

Reject the null hypothesis if one-sided p-value  $\leq 0.025$ .

The success criterion is a statistically significantly lower mean LogMAR DCIVA score for ZHR00 compared to ZCB00 ( $p \leq 0.025$ ). In addition, clinical significance will be determined by:

- The median DCIVA of the ZHR00 first eyes is at least 0.2 LogMAR.

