#### **10.4 RANDOMIZATION AND MASKING**

A randomization list will be created by the JJSV biostatistician for each investigative site and the randomization code will be uploaded into the electronic data capture system (EDC). Subjects will be randomized to the investigational Model ZHR00 IOL or the Model ZCB00 control IOL. Unmasked study personnel at the site will be trained to the randomization process through the EDC system and will randomize subjects after the

subject has signed the informed consent form, has met all eligibility criteria and the investigator has documented which eye will be the first implanted.

As part of the informed consent process, the investigator or delegate will explain to the subject the requirements of a randomized study and the differences expected between the two lens models in the study: the Model ZHR00 investigational lens and the Model ZCB00 control lens. The surgeon and the operative staff will know which lens type is implanted. There may also be site coordinators and other site study staff, such as those performing slit-lamp exams, who will be unmasked. Unmasked study site staff will be instructed not to disclose the lens type the subject received or to talk about the lens to any masked evaluators or to the study subjects.

The subjects and the study technicians performing the postoperative vision tests are to be masked through study completion. To maintain subject/technician-masking through the 6-month study exams, a masking plan will be tailored for each site to detail how lens assignment information will be concealed from masked technicians. Recommended steps to maintain masking include ensuring that all items pertaining to lens group assignment and lens implantation records are kept separately from all other study documents and subject medical records until after completion of the final study visit. For example, lens stickers (indicating the lens model implanted) may be kept in the operating room study notebook until completion of the final study visit, at which time they may be placed in the subject medical charts. In the meantime, temporary lens stickers (without lens model designations) may be used in the subject's medical chart.

To maintain subject masking, a temporary IOL implant identification card will be issued to the subject at the time of surgery. Following completion of the final study exam, each subject will be given the permanent IOL implant identification card.

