## **20.4 SITE ANALYSIS**

For the primary effectiveness and secondary endpoints, data will be reported by site. A mixed effects analysis will be used for primary DCIVA and both secondary endpoints. The mixed model will be used with IOL group as a fixed effect and site and site by group interaction as random effects. If the interaction term is significant at the 0.15 level then further examination of effects of site or further data stratification by site will be evaluated. Since there are no inferential statistics for the primary defocus curve endpoint, only graphs (defocus curve by site) will be presented for the site analysis. Baseline demographic data will also be reported by site.

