## **2.4 RANDOMIZATION**

A randomization list will be created by a JJSV biostatistician for each investigational site and the randomization code will be uploaded into the electronic data capture system (EDC). Subjects will be randomized to the investigational Model ZHR00 IOL or the Model ZCB00 control IOL. Unmasked study personnel at the site will be trained to the randomization process through the EDC system and will randomize subjects after the subject has signed the informed consent form, has met all eligibility criteria and the investigator has documented which eye will be the first implanted.

If a surgeon implants the wrong study lens, i.e., other than the one on the randomization schedule, the subject's study data will be analyzed according to the randomization schedule in the mITT population and will be analyzed according to the lens received in the safety population. The subject will be excluded from the Per-Protocol population analysis. If a surgeon implants a non-study IOL (e.g., due to capsule rupture prior to IOL implantation) or if the surgery is canceled in the few days between randomization and surgery (e.g., due to death, illness), the subject will not be part of the mITT, safety or Per-Protocol populations but will be placed in the intended IOL group (IOL group based on randomization schedule) and included in the worst case/best case sensitivity analyses.

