## 5.2 SECONDARY EFFECTIVENESS ENDPOINTS

### 5.2.1 MONOCULAR DISTANCE CORRECTED NEAR VISUAL ACUITY (DCNVA)

The first secondary endpoint is mean (LogMAR) first-eye, monocular, distance corrected near visual acuity under photopic conditions at 40 cm at 6 months postoperative. Results will be compared between lens groups for first eyes using one-sided, two-sample t-tests with alpha level of 0.025. The null hypothesis is that the mean LogMAR value for ZHR00 eyes is worse than or equal to that for control eyes. The alternative hypothesis is that the mean for ZHR00 eyes is better than that for control eyes.

$H_0: \mu_c - \mu_t \leq 0$  (ZHR00 is worse than (higher LogMAR) or equal to control)

$H_1: \mu_c - \mu_t > 0$  (ZHR00 is better (lower LogMAR) than control)

where

$\mu_t$  =mean DCNVA LogMAR for ZHR00

$\mu_c$  = mean DCNVA LogMAR for ZCB00

Reject the null hypothesis if one-sided p-value  $\leq 0.025$ .

The success criterion is a statistically significantly lower mean LogMAR value for ZHR00 compared to ZCB00 ( $p \leq 0.025$ ). In addition, clinical significance will be determined by:

- The median DCNVA of ZHR00 first eyes is at least 0.3 LogMAR

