### 5.3 SAFETY ENDPOINT

#### 5.3.1 MONOCULAR BEST CORRECTED DISTANCE VISUAL ACUITY (BCDVA)

The first safety endpoint is mean (LogMAR) first-eye, monocular, best corrected distance visual acuity (BCDVA) at 6 months postoperative. Results will be compared between lens groups for first eyes using a non-inferiority approach. The null hypothesis is that the mean difference (control minus test) between the control and test IOLs is  $\leq -0.1$  LogMAR (1 line) with the alternative hypothesis that the mean difference is  $> -0.1$  LogMAR. A two-sided, 90% confidence interval (CI) will be used for evaluation.

$$H_0: \mu_c - \mu_t \leq -0.1 \quad (\text{ZHR00 is worse than (higher LogMAR) or equal to control by } 0.1 \text{ LogMAR})$$

$$H_1: \mu_c - \mu_t > -0.1 \quad (\text{ZHR00 is better (lower LogMAR) than control by } 0.1 \text{ LogMAR})$$

where

$\mu_t$  = mean BCDVA LogMAR for ZHR00

$\mu_c$  = mean BCDVA LogMAR for ZCB00

Reject the null hypothesis if lower 2-sided 90% CI is  $> -0.1$ .

The success criterion is if the lower 2-sided 90% confidence interval for the difference between the IOLs is greater than -0.1.

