	ZHR00	ZCB00	ZHR00	ZCB00	ZHR00	ZCB00	
Monocular DCIVA by acuity line over time (No. and percent within each category)	X	X	X	X			SF
Monocular UCIVA by acuity line over time (No. and percent within each category)	X	X	X	X			SF
Monocular UCIVA at 66 cm (LogMAR) at 6M (N, Mean, SD, Median, Min., Max., 95% CI)	X	X	X	X			SF
Binocular UCIVA by acuity line at 6M (No. and percent within each category)					X	X	SF Bilateral subjects
Binocular UCIVA (LogMAR) ) at 6M (N, Mean, SD, Min, Max,95% CI)					X	X	SF Bilateral subjects
Monocular low contrast (10%) DCIVA (LogMAR) at 6M (N, Mean, SD, Median, Min., Max., 95% CI)	X	X	X	X			SF
Monocular low contrast (10%) DCIVA by acuity line at 6M	X	X	X	X			SF
Monocular low contrast (10%) BCIVA (LogMAR) at 6M (N, Mean, SD, Median, Min., Max., 95% CI)	X	X	X	X			SF
Monocular low contrast (10%) DCIVA by acuity line at 6M	X	X	X	X			SF
Visual Acuity – Near							
Monocular DCNVA at 40cm by Site (LogMAR) at 6M (N, Mean, SD, Median, Min., Max,)	X	X					SF
Monocular DCNVA by acuity line over time (No. and percent within each category)	X	X	X	X			SF
Monocular UCNVA by acuity line over time (No. and percent within each category)	X	X	X	X			SF
Monocular UCNVA (LogMAR) ) at 6M (N, Mean, SD, Median, Min, Max,95% CI)	X	X	X	X			SF
Binocular UCNVA by acuity line at 6M (No. and percent within each category)					X	X	SF Bilateral subjects
Binocular UCNVA (LogMAR) ) at 6M (N, Mean, SD, Median, Min, Max,95% CI)					X	X	SF Bilateral subjects
Visual Acuity –Distance							

	First Eyes	First Eyes	Second Eyes	Second Eyes	Subjects	Subjects	Comments (population used for analysis)
	ZHR00	ZCB00	ZHR00	ZCB00	ZHR00	ZCB00	
Monocular UCDVA by acuity line over time (No. and percent within each category)	X	X	X	X			SF
Monocular UCDVA (LogMAR) at 6M (N, Mean, SD, Median, Min, Max, 90% CI)	X	X	X	X			SF
Binocular UCDVA by acuity line at 6M (No. and percent within each category)					X	X	Bilateral SF
Binocular UCDVA (LogMAR) at 6M (N, Mean, SD, Median, Min, Max, 90% CI)					X	X	Bilateral SF
Monocular BCDVA by acuity line over time (No. and percent within each category)	X	X	X	X			SF and Best Case – 1 st eyes, SF – 2 nd eyes
Monocular BCDVA by Site at 6M (No and percent 20/40 or better)	X						SF
Listing at 6M for eyes with BCDVA worse than 20/40	X	X	X	X			SF
Other Defocus Curve							
Monocular defocus curve at 6M by site	X	X					SF

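### Randomisation is by site, but the analyses that decide DCIVA, DCNVA and BCDVA have no site term: a small precision gain is available at almost no cost

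*SAP*

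**What the plan says.** Allocation is organised by site. SAP 2.4 states: "A randomization list will be created by a JJSV biostatistician for each investigational site". Protocol 10.4 agrees: "A randomization list will be created by the JJSV biostatistician for each investigative site". Neither document says whether the lists are blocked or otherwise balanced within site.

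The deciding analyses carry no site term:

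- DCIVA (SAP 5.1.1): "Results will be reported by lens group for first eyes using one-sided, two-sample t-tests with alpha level of 0.025".
- DCNVA (SAP 5.2.1): "Results will be compared between lens groups for first eyes using one-sided, two-sample t-tests with alpha level of 0.025".
- BCDVA (SAP 5.3.1): "A two-sided, 90% confidence interval (CI) will be used for evaluation". The lower limit is compared with a margin of -0.1 LogMAR.

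Site enters in a separate analysis. SAP 2.6 specifies: "The mixed model will be used with IOL group as a fixed effect and site and site by group interaction as random effects". Protocol 20.4 gives its scope: "A mixed effects analysis will be used for primary DCIVA and both secondary endpoints". No success criterion refers to this model, and mean BCDVA is outside it. The one by-site BCDVA table in SAP Appendix I is "Monocular BCDVA by Site at 6M (No and percent 20/40 or better", marked for ZHR00 first eyes only, so no site-adjusted BCDVA difference between lenses is planned.

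For the mITT analyses of DCIVA and DCNVA, SAP 2.1 plans MCMC multiple imputation but does not name the variables in the imputation model.

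**The concern.** When a design balances the arms within site, differences between sites cancel out of the treatment contrast. A two-sample t-test still leaves those differences in its variance estimate. Its standard error is then too large, its true level falls below the stated one, and its interval is wider than needed. The same holds for the BCDVA interval. If site is also missing from the imputation model, some of this inefficiency carries into the combined mITT result.

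The SAP 2.6 model does not fill this role. Its random site-by-group term makes it a tool for examining heterogeneity and can widen the interval for the lens effect.

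What is at stake is precision and calibration. The error is towards caution, and only if two conditions hold that the documents do not settle: balance within site, and real differences between sites.

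**Working it through.** **Inputs from the plan.** 100 evaluable subjects per group (SAP 1); up to 10 sites (SAP 1); at least 20 implanted subjects per site (Protocol 8); SD 1.6 lines for DCIVA and DCNVA (SAP 7.1, 7.2) and 1.2 for BCDVA (SAP 7.3, read as lines), that is 0.16 and 0.12 LogMAR; 10% drop-out (SAP 7.4).

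**Assumed, because the plan does not give it.** The share ρ of total variance lying between sites: 5, 10 and 20%. Layout: 10 sites of 20, exactly 1:1 within site for the blocked case.

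**The plan's own figures.** A noncentral t with 198 df gives 99.3% power at one line (SD 1.6, one-sided 0.025). BCDVA non-inferiority power (SD 1.2, margin one line, true difference zero, one-sided 0.05) exceeds 99.9%. Both satisfy the stated figure of over 90%.

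**Blocked lists, standard error.** The lens difference has true variance (1-ρ)·SD²·(2/100). The t-test's pooled within-arm variance also keeps site variation: with 10 subjects per site per arm, its expectation is SD²·[(1-ρ) + ρ·(10×9)/99]. The ratio of unadjusted to adjusted SE is therefore about sqrt{[(1-ρ) + 0.909ρ]/(1-ρ)}:

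- ρ = 5%: sqrt(0.9955/0.95) = 1.024
- ρ = 10%: sqrt(0.9909/0.90) = 1.049
- ρ = 20%: sqrt(0.9818/0.80) = 1.108 (simulated 1.107)

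**Blocked lists, true level.** Simulation, 1,000,000 null trials per setting:

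| ρ | t-test, nominal 0.025 | with site | BCDVA CI, nominal 0.05 | with site |
|---|---|---|---|---|
| 0 | 0.025 | 0.025 | 0.050 | 0.050 |
| 5% | 0.022 | 0.025 | 0.046 | 0.050 |
| 10% | 0.020 | 0.025 | 0.042 | 0.050 |
| 20% | 0.015 | 0.025 | 0.035 | 0.050 |

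**Decision thresholds (SD held at the planned value).**

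- DCIVA/DCNVA difference needed for significance. Unadjusted: 1.972 × 0.16 × sqrt(2/100) = 0.0446 LogMAR. With site, on 198 - 9 = 189 df: 1.973 × 0.16 × sqrt(2/100) × sqrt(1-ρ) = 0.0435, 0.0423 and 0.0399.
- BCDVA 90% half-width. Unadjusted: 1.653 × 0.12 × sqrt(2/100) = 0.0280. With site: 0.0273, 0.0266 and 0.0251.
- Largest BCDVA deficit that still passes (0.1 minus the half-width): 0.0720 unadjusted; 0.0727, 0.0734 and 0.0749 with site.

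Even at 20%, a verdict would on average change only for DCIVA or DCNVA differences of about 0.040 to 0.045, or a BCDVA deficit of about 0.072 to 0.075. At 5% the bands shrink to about 0.0435-0.0446 and 0.0720-0.0727.

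**Unblocked lists.** The t-test keeps its level (0.0243 and 0.0257 at 10 and 20%). Adjusting for site raises the SE by about 2.4% when sites do not differ, breaks even near 5%, and lowers the SE by about 2.4% at 10% and 7.5% at 20%.

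**Other layouts, blocked.** Four sites of 50 give SE ratios of 1.020, 1.041 and 1.089. Uneven sites (50, 36, 30, 24, 20, 20, 10, 10) with the two smallest pooled give 1.021, 1.043 and 1.093, against 1.022, 1.046 and 1.100 unpooled.

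**Imputation.** 224 subjects, 10% missing completely at random, blocked, 20 imputations, 20,000 trials per setting (Monte Carlo SE 0.001). True level at nominal 0.025:

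| ρ | site nowhere | site in analysis only | site in both |
|---|---|---|---|
| 10% | 0.021 | 0.024 | 0.024 |
| 20% | 0.016 | 0.021 | 0.024 |

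**The case against.** The strongest reply is that nothing here is invalid. A two-sample t-test in a 1:1 trial is a legitimate prespecified choice, any error is conservative, and power is ample. The gain is also tiny on the clinical scale. One letter is 0.02 LogMAR (SAP Appendix II), so at a 20% site share the significance threshold moves by 0.0446 - 0.0399 = 0.0047, about a quarter of a letter, and the BCDVA half-width by 0.0029, about 0.15 letter. The site share may well be modest, since the protocol standardises the M&S testing system, refraction technique, lighting checks and masked testers. With unblocked lists and little site variation, the adjusted model is slightly less precise. Site is already modelled for DCIVA and both secondary endpoints in SAP 2.6.

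Most of this stands and sets the weight of the point: it is an improvement to consider. It does not remove the point. The SAP 2.6 model is not the success test, has a different structure and leaves out mean BCDVA. Standardised testing may reduce site differences, but the documents do not quantify what remains. The loss in the unblocked case is small and is counted in the cost of the change.

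**Conclusion.** The concern holds, as a point to consider, with medium confidence. Allocation is by site, the three deciding analyses ignore site, and no site-adjusted BCDVA comparison is planned.

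If lists are balanced within site and 5 to 20% of the variance lies between sites, the unadjusted standard error is about 2 to 11% larger than the site-adjusted one. The nominal 0.025 tests run at about 0.022 to 0.015, and the nominal 0.05 BCDVA criterion at about 0.046 to 0.035. If lists are unblocked, or sites do not differ, the stated levels are correct. The variance shares and the 10 × 20 layout are assumptions. Conclusions at the planned effect sizes would not be expected to change.

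**What to change.** Make the decisive analysis for DCIVA, DCNVA and the BCDVA 90% interval a linear model with lens group and site as main effects, keeping the present alpha levels and margin. In addition:

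- For DCIVA and DCNVA, put lens group and site in the imputation model and in the model fitted to each imputed data set, then combine with MIANALYZE.
- Use the same analysis model in the worst-case, best-case and tipping-point analyses.
- Keep the unadjusted t-tests and interval as supportive. Fisher's test for spectacle independence can stay.
- State in SAP 2.6 that the random site-by-group model serves only to examine site heterogeneity, and add mean BCDVA to it.
- Fix a pooling rule before database lock. For example, sites with fewer than 20 implanted subjects (the Protocol 8 minimum) form one stratum, and a lone small site joins the next smallest.
- State in SAP 2.4 whether lists are blocked within site. Block size can stay in a restricted file.

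If the sponsor keeps the unadjusted tests as decisive, the minimum is the blocking statement in SAP 2.4 and mean BCDVA in SAP 2.6.

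The cost is SAP wording and minor programming, with no change to enrolment, and up to 9 degrees of freedom. With blocked lists and no site differences, power at one line stays at 99.3%. With unblocked lists and no site differences, it falls from 99.25% to 99.01% at one line, and from 59.2% to 57.2% at half a line, an effect the plan does not target.
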